### 5.2.1 Secondary Analysis

- Descriptive statistics of the actual values (original unit and log10 transformed values) and the change from baseline (log10 transformed values) over time for qualitative viral activity parameters according to the specification described in section 2.6 will be included.
- LS means (SE) of change from baseline (and 95% confidence interval) for qualitative viral activity parameters per time point and overall based on log10 transformed values will be analyzed by subject population and part using mixed effects model for repeated measures similar as described in section 5.2.1.1.. Also P-values for treatment, time, their interaction and overall will be added.
- LS means (SE) of change from baseline (and 95% confidence interval) for qualitative viral activity parameters (except for HBeAg) per time point and overall based on log10

---

transformed values will be analyzed by subject population, part and by HBeAg status using mixed effects model for repeated measures similar as described in section 5.2.1.1. Also P-values for treatment, time, their interaction and overall will be added.

- A tabulation of the proportion of subjects with virological breakthrough during 24 week treatment and during 48 week treatment (only subjects with treatment extension) will be included.
- A tabulation of the proportion of subjects with viral relapse will be provided. For the purpose of the analysis, the denominator will only include those subjects with values Yes and No.
- Descriptive statistics of the maximum decrease from baseline ( $\log_{10}$  transformed values) over time for qualitative viral activity parameters according to the specification described in section 2.6 will be included.
- A tabulation of the status change from baseline at week 24 and at week 48 (only subjects with treatment extension) will be displayed by viral activity parameter.
- A tabulation of the proportion of subjects who meet the criteria of response categories per time point defined in section 5.3.1 will be displayed by viral activity parameter.
- A tabulation of the proportion of subjects who meet the criteria of response categories per period defined in section 5.3.1 (additional information in the table) will be displayed by viral activity parameter.
- A tabulation of the qualitative result of HBeAg and HBsAg per timepoint (week 24 and week 48) will be included.
- A tabulation of the biochemical response per time point will be included.
- All individual values will be presented in subject listings: (1) including all subjects, (2) including subjects with viral breakthrough during 24 weeks or 48 weeks treatment (only subjects with treatment extension) and (3) including subjects with viral relapse.
- Mean (+/- SE) plots of the actual ( $\log_{10}$  transformed) values for all viral activity parameters will be presented by parameter.
- Mean (+/- SE) plots of the change from baseline for all viral activity parameters will be presented by parameter.
- A plot representing all actual ( $\log_{10}$  transformed) values of all viral activity parameters for each subject will be included. One graph per subject.
- The actual ( $\log_{10}$  transformed) values over time are plotted per the viral activity parameter. Each line will represent one subject.
- The change from baseline ( $\log_{10}$  transformed values) over time are plotted per the viral activity parameter. Each line will represent one subject.

---

The proportion of subjects for the secondary categorical endpoints below will be categorized by treatment group, HBeAg status and overall (pool HBeAg status) during study treatment and follow-up and where appropriate the difference between proportions and Clopper-Pearson 95%CIs may be calculated using a chi-square test of equal proportions.

- The proportion of subjects with a viral breakthrough
- The proportion of subjects with HBsAg seroclearance
- The proportion of subjects with HBsAg seroconversion
- The proportion of subject with viral relapse
- The proportion of subjects with HBsAg reduction
- The proportion of subjects with HBeAg reduction
- The proportion of subjects with HBVDNA reduction
- The proportion of subjects with HBV RNA reduction
- The proportion of subjects with biochemical relapse
- The proportion of subjects with clinical viral relapse

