## **11.11. Interim Analyses**

At the Week 12 interim analyses, the sponsor study team will remain blinded to the randomization codes (unless the DRC recommends unblinded analyses, see below) and data will be analyzed using dummy identification and aggregated efficacy summary statistics. At the unblinded Week 24 interim analyses (and subsequent analyses), the sponsor study team members involved in safety monitoring of the treatment extension phase as well as the investigator, site personnel and subjects will remain blinded. The sponsor study team members involved in safety monitoring of the treatment extension phase will remain blinded to the treatment/randomization codes until the end of the treatment extension phase while the investigator, site personnel and

subjects will remain blinded until the end of the study. Note that blinding does not apply to the JNJ-56136379 monotherapy arms.

Interim analyses, encompassing efficacy, safety, and pharmacokinetics, may be conducted for **Part A** and **Part B** at study Week 12, 24, 36, 48 and 72 separately when at least 80% of subjects have completed the respective visit (ie, Week 12, Week 24 for all subjects, FU Week 12/Week 36 and FU Week 24/Week 48 for subjects receiving 24/48 weeks of study treatment, and, FU Week 24 for subjects receiving 48 weeks of study treatment, respectively) or have discontinued earlier (see also [Figure 1](#)).

At the sponsor's discretion, these interim analyses may also be performed separately by subject population (currently not being treated versus virologically suppressed) in case recruitment rates differ between the subject populations.

Additional interim analyses may be performed at the sponsor's discretion to support decision making for further development of JNJ-56136379 and to support interactions with health authorities.

A final analysis will be performed when all subjects in the study have completed the last study-related follow-up visit or have discontinued earlier.

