### 5.2.1 Parameter Definitions

The following parameters will be derived as follows:

*Viral breakthrough during 24 weeks of treatment (all subjects), during 48 weeks of treatment (subject with treatment extension) and during NA follow up for all subject who switch to NA-treatment during follow-up:*

HBV virological breakthrough is defined as having a confirmed on-treatment HBV DNA increase by  $>1$  log10 from nadir level (lowest level reached during 24/48 weeks treatment) or a confirmed on-treatment HBV DNA level  $>200$  IU/mL in subjects who had HBV DNA level below the lower limit of quantification (LLOQ) of the HBV DNA assay.

The proportion of subjects with a viral breakthrough is defined as follows:

---

- 0 (No) = subject has not had a viral breakthrough (see definition above) up to the considered time point
- 1 (Yes) = subject has a viral breakthrough at the considered time point or has had a viral breakthrough before (regardless of the HBV DNA result at the considered time point)
- 2 (No: ongoing): subject has not had a viral breakthrough (see definition above) up to the last time point but is still ongoing (only for interim analysis)

Confirmed means that the criterion should be fulfilled at 2 or more consecutive time points or at the last observed time point on-treatment. On-treatment means in the treatment phase, except for the baseline record.

The proportion of subjects with a viral breakthrough during initial 24- or 48-weeks treatment but still on NA Treatment (Yes / No)

Note: For Viral breakthrough during NA follow up, only subject on NA treatment will be include in the denominator.

*Viral relapse* is defined in the follow-up phase as follows:

- 1 (Yes) = viral relapse: confirmed  $\geq 2000$  IU/mL quantifiable.
- 0 (No) = no viral relapse: at least one post-treatment measurement available and not a viral relapse
- 2 (Not applicable) = no post-treatment HBV DNA measurements available
- 3 (No: ongoing) = no viral relapse: at least one post-treatment measurement available and not a viral relapse but still ongoing (only for interim analysis)

Confirmed means that the criterion should be fulfilled at 2 or more consecutive time points or at the last observed time point.

Note: viral relapse will only be assessed for those subjects who at the actual end of treatment have HBV DNA  $< 20$  IU/ml detectable/ undetectable.

*Biochemical relapse* is defined in the follow-up phase as follows:

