- 1 (Yes) = biochemical relapse: confirmed  $ALT > 2 * ULN$ .
- 0 (No) = no biochemical relapse: at least one post-treatment measurement available and not a viral relapse
- 2 (Not applicable) = no post-treatment ALT measurements available

---

- 3 (No: ongoing) = no biochemical relapse: at least one post-treatment measurement available and not a biochemical relapse but still ongoing (only for interim analysis)

Confirmed means that the criterion should be fulfilled at 2 or more consecutive time points or at the last observed time point.

Note: biochemical relapse will only be assessed for those subjects who at the actual end of treatment have  $ALT \leq ULN$ .

*Clinical viral relapse is defined as follow:*

- 1 (Yes) = if both viral and biochemical relapse
- 0 (No) = otherwise and not ongoing
- 2 (Not applicable) = no post-treatment measurements available
- 3 (No: ongoing) not both viral and biochemical relapse but still ongoing (only for interim analysis)

Note: clinical viral relapse will only be assessed for those subjects who at the actual end of treatment have  $HBV\ DNA < 20\ IU/ml$  detectable/ undetectable and  $ALT \leq ULN$ . *Seroconversion of HBsAg (all subjects) / HBeAg (positive subjects) at week 24 of the treatment and at week 48 of the treatment (only subjects with treatment extension)* is defined as a confirmed loss of HBsAg/HBeAg at week 24/48 of the treatment. Loss is defined as a baseline HBeAg /HBsAg (qualitative) with a "REPEAT REACTIVE, CONFIRMED" or "POSITIVE" result and a post-baseline assessment with a "NEGATIVE" result.

*Seroconversion of HBsAg (all subjects) /HBeAg (positive subjects) at week 24 of the treatment and at week 48 of the treatment (only subjects with treatment extension)* is defined as:

- Use the selected time point for the week 24 or 48 visit as described in 2.3.
- A confirmed loss of HBsAg/HBeAg at week 24/48-of the treatment (i.e. seroclearance)
- and an appearance of Anti-HBs/Anti-HBe.

Loss is defined as a baseline HBeAg /HBsAg (qualitative) with a "REPEAT REACTIVE, CONFIRMED" or "POSITIVE" result and a post-baseline assessment with a

---

"NEGATIVE" result. Appearance is defined as a baseline Anti-HBs/ Anti-HBe (qualitative) with a "NEGATIVE" result and a post-baseline assessment with a "POSITIVE" result. Both criteria should be fulfilled.

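### At interims held during follow-up, the viral relapse denominator, read literally, drops ongoing relapse-free subjects but keeps ongoing relapsers, so the proportion is biased upward

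*SAP*

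**What the plan says.** SAP Section 5.3 (Parameter Definitions) assesses viral relapse in the follow-up phase, in subjects whose HBV DNA was below 20 IU/mL at the actual end of treatment. The codes are:

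- Code 1: "1 (Yes) = viral relapse: confirmed" HBV DNA at or above 2000 IU/mL. It is not split by whether the subject is still being followed.
- Code 0: "0 (No) = no viral relapse: at least one post-treatment measurement available and not a viral relapse".
- Code 2: "2 (Not applicable) = no post-treatment HBV DNA measurements available".
- Code 3, labelled as an ongoing No: at least one post-treatment value, "not a viral relapse but still ongoing (only for interim analysis").

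On confirmation: "Confirmed means that the criterion should be fulfilled at 2 or more consecutive time points or at the last observed time point". One high latest value therefore makes an ongoing subject a Yes.

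Section 5.3 (Secondary Analysis) provides a tabulation of the viral relapse proportion and states: "For the purpose of the analysis, the denominator will only include those subjects with values Yes and No". It also allows differences between proportions and Clopper-Pearson intervals for this endpoint.

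Biochemical relapse and clinical viral relapse have the same code 3; for the latter it reads "not both viral and biochemical relapse but still ongoing (only for interim analysis"). Neither has a written denominator rule.

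Protocol Section 11.11 allows interims by study part at Weeks 12, 24, 36, 48 and 72, "separately when at least 80% of subjects have completed the respective visit" or have discontinued earlier. Week 72 is follow-up Week 24 for subjects treated for 48 weeks. Under Protocol Section 3.1, subjects who meet the treatment completion criteria are followed for 48 weeks off treatment (Schedule 2); the others are followed for 24 weeks (Schedule 1).

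**The concern.** Whether an ongoing subject enters the proportion depends on the outcome being measured. A relapser enters as soon as the relapse is recorded; a relapse-free subject enters only when follow-up ends. A relapser who restarts NA under the Protocol's re-treatment criteria remains in Schedule 2 follow-up and stays in the count.

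Relapse after stopping all treatment bears directly on the finite-treatment question in Protocol Section 1.4. Both documents say that additional interims may be used to support development decisions and contacts with health authorities. SAP Section 5 presents efficacy by follow-up type, so the treatment-free group, with the longest follow-up, is shown on its own. SAP Table 5 includes no relapse endpoint, so no censored analysis stands beside the proportion.

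**Working it through.** **Inputs.** The codes and denominator rule are from SAP Section 5.3, interim timing from Protocol Section 11.11, and follow-up lengths from Protocol Section 3.1. The documents give no relapse rate, no number entering Schedule 2, no dropout rate and no spread of entry into follow-up. They state no figure for this endpoint that could be reproduced. These inputs are assumed below.

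**Step 1: what the rule computes.** Let n1, n0 and n3 be the numbers with codes 1, 0 and 3, and N = n1 + n0 + n3. Put r = n1/N (relapsed to date) and c = n0/(n0 + n3) (share of relapse-free subjects whose follow-up has ended).

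Reported proportion = n1/(n1 + n0) = r/[r + (1 - r)c].

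Because c is at most 1, this is never below r. It equals r when c = 1. If anyone has relapsed and c = 0, it is 100%.

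**Step 2: a small example (assumed: 20 assessable subjects, 4 relapsed, 20% to date).**

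| Relapse-free and ongoing | Reported under the rule |
|---|---|
| 0 | 4/20 = 20% |
| 4 | 4/16 = 25% |
| 8 | 4/12 = 33% |
| 12 | 4/8 = 50% |
| 16 | 4/4 = 100% (95% CI 39.8 to 100%) |

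Keeping code 3 in the denominator gives 4/20 = 20% (95% CI 5.7 to 43.7%) in every row.

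**Step 3: dependence on r and c.**

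| r | c = 0.1 | c = 0.5 | c = 0.8 |
|---|---|---|---|
| 5% | 34.5% | 9.5% | 6.2% |
| 20% | 71.4% | 33.3% | 23.8% |
| 40% | 87.0% | 57.1% | 45.5% |

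**Step 4: Schedule 2 at the Week 72 interim.** Simulation assumptions: 30 subjects entering follow-up uniformly over 30 weeks, constant relapse hazard, 5% dropout by follow-up Week 24, cut-off when 80% could have reached follow-up Week 24.

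- 20% relapse risk by follow-up Week 24: about 80% reported against 25% to date.
- 40% risk: about 91% reported against 48% to date.

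Solving Step 1 for c, with p the reported proportion, gives c = r(1 - p)/[p(1 - r)]. For the first case, 0.25 × 0.20/(0.80 × 0.75) = 0.083; for the second, 0.48 × 0.09/(0.91 × 0.52) = 0.091. Fewer than one relapse-free subject in ten has finished, as expected halfway through a 48-week follow-up.

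A second simulation, with no dropout and 20% risk, gives 100%, 100% and 57% for entry spread over 12, 26 and 52 weeks, against 23%, 25% and 28% to date.

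**Step 5: 24-week follow-up.**

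- When 80% have reached follow-up Week 24, 40% risk gives 44% against 38%. The implied c is 0.38 × 0.56/(0.44 × 0.62) = 0.78. A 20% risk gives 23 to 24% against 19 to 20%; a 5% risk gives 5.9% against 4.8%.
- When 80% have reached follow-up Week 12, the result depends heavily on the spread of entry. With 20% risk and no dropout, the rule gives 100%, 37% and 26% for entry over 12, 26 and 52 weeks, against 13%, 15% and 16% to date.

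Once every subject has finished, c = 1 and the bias is zero.

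**The case against.** The best defence is that the sentence is ambiguous. Code 0 for viral relapse asks only for a post-treatment value and no relapse, which an ongoing relapse-free subject satisfies. Code 3 is itself labelled a kind of No, and the sentence may be meant only to remove code 2. That possibility stands. Against it, code 3 is a separate value, and code 0 for clinical viral relapse expressly requires that the subject is not ongoing. If codes 0 and 3 were merged, the outcome-dependent exclusion would go, but a subject two weeks into follow-up would count as a full non-relapser. The text needs settling under either reading.

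There is also mitigation. SAP Table 4 tabulates HBV DNA below 2000 IU/mL by time point, relapsers are listed, and every subject is plotted. The Data Presentation Specifications, which select the interim tables, are not among the documents, so it is not shown that this table is run at a given interim. The study is exploratory, without formal hypothesis testing. These points limit the consequence but leave the rule as it is.

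A reader might infer more than the documents support:

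- **That every interim is driven towards 100%.** At Weeks 12 and 24 few subjects are in follow-up, and near the end of 24-week follow-up the inflation is small. Values near 100% need c close to zero.
- **That Schedule 2 has a follow-up Week 12 interim at 80%.** The Protocol ties follow-up Week 12 to subjects treated for 24 weeks. SAP Section 1 requires all subjects to have completed that visit, and SAP Section 3.1 makes that interim discretionary.
- **That arms with slower accrual look worse.** Schedule 2 is not an arm, and arms are randomised concurrently within each part and population.
- **That 40% relapse is realistic for Schedule 1.** Those subjects should be on NA, so the lower-risk figures in Step 5 may be nearer.

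**Conclusion.** The concern holds for viral relapse at interims held while subjects are still in follow-up. On the literal reading the rule makes inclusion depend on outcome, and the reported proportion is never below the proportion relapsed to date. That direction follows from the SAP's own codes and needs no assumed rate.

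The size does need assumptions. It is largest for the treatment-free Schedule 2 cohort at Week 72: about 80 to 91% against 25 to 48% to date for assumed risks of 20 to 40% by follow-up Week 24, moving with the spread of entry and dropout. It falls to a few points when 24-week follow-up is nearly complete and to nothing when it is complete.

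One case beyond the interims needs stating. SAP Section 3.1 sets the final analysis at follow-up Week 24, when Schedule 2 subjects may still be followed to Week 48, whereas Protocol Section 11.11 waits for the last follow-up visit. The SAP does not say how such subjects would be coded there. For biochemical and clinical relapse the shared code 3 creates the same opening, but applying the Yes/No restriction to them would be inference.

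**What to change.** Replace the denominator sentence in SAP Section 5.3 so that only code 2 is excluded, and code 3 is never dropped while ongoing Yes subjects are kept.

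At interims, report one of the following:

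- the proportion relapsed by a stated follow-up week, among subjects whose end-of-treatment date allows that visit by the cut-off; or
- a Kaplan-Meier estimate from end of treatment, censored at the last HBV DNA assessment, using the censoring approach that Table 5 already applies to virological breakthrough.

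State that the same rule covers biochemical relapse (censored at the last ALT assessment if Kaplan-Meier is used) and clinical viral relapse. State also how Schedule 2 subjects still in follow-up are handled at the SAP Section 3.1 final analysis.

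The minimum change is a sentence of SAP text; the fuller one adds a table per relapse endpoint. Neither needs new data or visits.

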#### **5.4. Dose response Analysis**

The dose-response of the effect of JNJ-56136379 in an NA background regimen on the Week 24 HBsAg change from baseline will be studied using the combined data of Part A and Part B. The data will consist of three dose groups:

- Placebo: pooled control arms of Part A and Part B
- Low Dose (75 mg): JNJ-56136379+NA arm of Part A
- High Dose (to be determined): JNJ-56136379+NA arm of Part B

The dose-response analysis will be carried out by subject population (currently not treated or virologically suppressed by current NA treatment), irrespective of HBeAg status, and also by HBeAg status within each population.

The presence of a dose-response signal will be assessed using a multiple contrast test, following the MCP-Mod methodology (REF: Bjornkamp et al. 2009). In this approach, a candidate set of plausible dose-response shapes need to be defined. As only 2 JNJ-

---

[figure not shown]
56136379 doses (and placebo) are studied in the current trial, possible dose-response shapes to consider are determined by the relative effect of the low dose compared to the high dose and the spacing of the dose. Three monotone dose-response shapes are included in the candidate model set:

- Linear
- Emax: the effect of the low dose is higher than expected from a linear relationship
- Exponential: the effect of the low dose is less than expected from a linear relationship

These models are parametrized as follows (using notation as in Bornkamp et al., 2009):

- Linear model (no parameters)
- Emax ( $ED_{50}=0.20$ )
- Exponential ( $\delta=0.18$ )

The three dose response shapes are illustrated in Figure 1.

**Figure X2: Multiple Contrast Test Candidate Model Set**

The significance of the dose-response signal associated with each candidate model will be determined using trend tests with model-specific optimal contrast coefficients. The maximum of the candidate model trend test statistics will be used to evaluate the presence of a dose-response signal, properly accounting for multiplicity at an overall level of 5% (1-sided) using MCP-Mod methodology.

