**Part A:**

Approximately 70 subjects who are currently not being treated for their CHB infection will be randomized in a 3:1:3 ratio to receive one of the following treatments:

- Treatment Arm 1: JNJ-56136379 (N=30) (open-label)

After full recruitment, this treatment arm was discontinued early per Protocol Amendment 4. All subjects were to stop further dosing with JNJ-56136379 75 mg, start treatment with NA, and enter the post-treatment follow-up phase (Schedule 1).

- Treatment Arm 2: Placebo + NA (ETV or TDF) (N=10)
- Treatment Arm 3: JNJ-56136379 + NA (ETV or TDF) (N=30)

At the same time, approximately 40 subjects who are virologically suppressed by current NA treatment will be randomized in a 1:3 ratio to receive one of the following treatments:

- Treatment Arm 4: Placebo + NA (ETV or TDF) (N=10)
- Treatment Arm 5: JNJ-56136379 + NA (ETV or TDF) (N=30)

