### **11.2. Sample Size Determination**

As this is an exploratory, hypothesis-generating study, no formal statistical hypothesis testing will be performed.

The adequacy of the sample size for the different parts of the study has been assessed by evaluating the performance of the planned analyses on the primary endpoint (mean HBsAg change from baseline at Week 24) comparing JNJ-56136379+NA with placebo+NA as outlined in Section 11.3. Baseline is defined as the last assessment prior to the first intake of study drugs (JNJ-56136379/NA/placebo) on Day 1.

Power was assessed using simulations (10,000 replicates per scenario) with means and SDs for the placebo+NA and JNJ-56136379+NA arms as listed in Table 7. Mean and SD may depend on HBeAg status at baseline and prior treatment (currently not being treated or virologically

suppressed). Treatment with JNJ-56136379 was set to result in one additional mean  $\log_{10}$  IU/mL decline in HBsAg from baseline at Week 24. Data were simulated from mixture distributions which reflect the skewed distributions which are typical HBsAg decline data. It is assumed that HBeAg-positive subjects will enroll slower than HBeAg-negative subjects, particularly in virologically suppressed subjects. Therefore, the aim is to have at least 40% HBeAg-positive subjects currently not being treated and 30% HBeAg-positive virologically suppressed subjects.

For the dose-response modeling (multiple contrast test) the placebo+NA arms of Parts A and B will be pooled and the HBeAg subgroups will be pooled per dose. Assuming the treatment effect does not depend on HBeAg status, the power to detect a dose-response signal ( $\alpha=0.10$ , one-sided) depends on the assumed effect of the low dose: ranging from 91% when the low dose has no effect to 99% when the low dose has the same effect as the high dose. Sensitivity analyses will be done investigating differences across Parts A and B and differences between the two HBeAg subgroups.

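### The SAP tests the dose-response signal at one-sided 5%, but the protocol's 91 to 99% power was computed at one-sided 10%, so the stated power belongs to a different test.

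*SAP*

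**What the plan says.** Protocol Section 11.2, repeated in the synopsis, says that "the power to detect a dose-response signal ( $\alpha=0.10$ , one-sided) depends on the assumed effect of the low dose" and gives the result as "ranging from 91% when the low dose has no effect to 99% when the low dose has the same effect as the high dose". For this analysis "the placebo+NA arms of Parts A and B will be pooled and the HBeAg subgroups will be pooled per dose".

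SAP Section 5.4 describes the same analysis: Week 24 HBsAg change from baseline, three groups (pooled placebo+NA, low dose+NA, high dose+NA) and three candidate shapes. The largest of the three trend statistics is judged by "properly accounting for multiplicity at an overall level of 5% (1-sided) using MCP-Mod methodology".

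SAP Section 1.5 contains only a pointer to protocol Section 11.2. Protocol Section 11.3.1 describes the test without naming a level, and the opening of protocol Section 11 leaves specific details to the SAP. In SAP Appendix 2 the test call carries no level either.

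**The concern.** Power is a property of a test at a stated level. If the level is halved and nothing else changes, power must fall, so a figure computed at 10% cannot justify a test run at 5%. The SAP adopts that figure by reference.

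Two things are at stake. First, the risk of missing a real signal is larger than the plan says, mostly when the low dose is inactive, which is the least favourable case the protocol names. Second, an adjusted p-value between 0.05 and 0.10 would be a signal at the protocol's level and no signal at the SAP's. Choosing between them after seeing the result would be post hoc.

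**Working it through.** **Inputs**

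- One-sided level: 0.10 (protocol 11.2) against 0.05 (SAP 5.4).
- Group sizes per subject population: placebo+NA 10 in each part, pooled to 20; JNJ-56136379+NA 30 per dose (protocol 3.1). SAP 5.4 runs the test within each population, so 20/30/30.
- Effect: 1 log10 additional decline. Placebo+NA −0.05 (SD 0.4), active −1.05 (SD 2.16) (protocol Table 7).
- In untreated subjects the placebo SD pooled over HBeAg status is √(0.4×0.6² + 0.6×0.4² + 0.4×0.6×0.30²) = √(0.144 + 0.096 + 0.0216) = 0.51. It was run as a variant.
- Dose ratio 75/250 = 0.30. Shapes on relative dose: linear, Emax with ED50 0.20, exponential with delta 0.18 (SAP 5.4 and Appendix 2).
- Not given: the mixture. The protocol says only that "Data were simulated from mixture distributions which reflect the skewed distributions which are typical HBsAg decline data".

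**Assumed mixture.** A fraction p of the active arm has an extra decline d, with p·d = 1 and 0.4² + p(1−p)d² = 2.16². Hence (1−p)/p = 4.6656 − 0.16 = 4.51, so p ≈ 0.18 and d ≈ 5.5. This is about the smallest p that SD 2.16 allows. Larger p was also run, matched to the same mean and SD.

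**Test.** For each shape k, T_k = Σc_ki·m_i / √(Σc_ki²·s_i²/n_i), where m_i is the mean decline in group i, so a decline counts as benefit. The maximum of the three is referred to their joint normal distribution. The contrasts are weighted by the group standard errors, because the Appendix 2 call supplies the models and the variance matrix but not the contrasts. An inactive low dose was given the placebo distribution.

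**Step 1: reproduce the protocol, then change only the level** (10,000 trials per scenario)

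| Placebo SD, responders | Low inactive, 10% | Low inactive, 5% | Low = high, 10% | Low = high, 5% |
|---|---|---|---|---|
| 0.4, 20% | 0.916 | 0.810 | 0.983 | 0.957 |
| 0.4, 25% | 0.923 | 0.814 | 0.988 | 0.968 |
| 0.51, 20% | 0.904 | 0.779 | 0.973 | 0.942 |
| 0.51, 25% | 0.912 | 0.798 | 0.976 | 0.948 |

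The 10% columns lie within 2 points of the stated 91% and 99%. Shorter runs with 18% and 30% responders give 0.90 to 0.91 falling to 0.79 to 0.80 when the low dose is inactive. Letting the inactive low dose keep SD 2.16 widens the 5% range to 0.78 to 0.84.

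**Step 2: a check without an assumed mixture.** With contrasts for 2:3:3 allocation, the critical value of the maximum of three rises from 1.53 to 1.875. Shift the protocol's own powers by that amount:

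- Low dose inactive: Φ(1.341 + 1.53 − 1.875) = Φ(0.996) = 0.84.
- Low = high: Φ(2.326 + 1.53 − 1.875) = Φ(1.981) = 0.976.

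**Step 3: other assumptions**

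| Variant | Low inactive, 10% to 5% | Low = high, 10% to 5% |
|---|---|---|
| Normal data, low-dose SD 0.4 | 0.83 to 0.72 | 0.97 to 0.94 |
| Normal data, low-dose SD 2.16 | 0.86 to 0.77 | 0.97 to 0.94 |
| 25% responders, fixed 2:3:3 contrasts | 0.96 to 0.90 | 0.98 to 0.94 |
| More skewed (gamma) responses | 0.98 to 0.92–0.93 | not tabulated |

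The loss with an inactive low dose runs from about 5 points (gamma) through 7 (Step 2) to 12.5 (0.904 − 0.779).

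**The case against.** The study is declared exploratory, with no formal hypothesis testing. Dose-response is evaluated in addition to three main comparisons, and no go/no-go rule depends on it. The SAP level is the stricter one, so false-positive risk does not rise. The protocol names 10% only in its sample-size text and leaves analysis details to the SAP, so 5% may be deliberate. The mixture is unknown, and the one used was chosen because it matches the stated power. Under gamma responses, power with an inactive low dose stays at 0.92 to 0.93 at 5%, inside the stated range.

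Much of this stands. It limits the consequence, it means 10% is not automatically the right choice, and it means the simulated values should not be copied into the plan. It does not remove the mismatch: the SAP still sets a level and a rule for declaring a signal, and the protocol still quotes power for that rule at another level. The direction needs no mixture. The gamma case does not reproduce the protocol, since it starts at 0.98 rather than 0.91, and it still loses 5 to 6 points.

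The missing level in Appendix 2 is a side point. The SAP text does state 5%, and the SAP introduction also names a SAS procedure for dose-response modelling.

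**Conclusion.** The concern holds. The same test is powered at one-sided 10% in the protocol and run at one-sided 5% in the SAP, and nothing reconciles the two.

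With an inactive low dose, power at 5% is about 84% by the critical-value shift and about 78 to 84% under the mixtures close to the protocol's figures. The miss rate goes from about 9% to 16–22%, roughly double. With equal doses, power stays at about 94 to 98%.

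The sizes rest on 20/30/30 subjects per population and, for the simulations, on an assumed responder mixture. The by-HBeAg dose-response tests in SAP 5.4 have fewer subjects and are not covered by the stated power at either level. This is a mismatch between documents that should be corrected; it does not undermine the trial.

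**What to change.** Use one level in both documents and settle it before unblinded data are analysed. There are two ways:

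- Set SAP Section 5.4 to an overall one-sided 10%, the level to which the stated 91 to 99% belongs.
- Keep 5% and restate the dose-response power at 5%. The sponsor should rerun its own simulation with its own mixture. The values here (about 78 to 84% for an inactive low dose and about 96% for equal doses) show what to expect.

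In either case, write the chosen level explicitly into the test call in Appendix 2. The cost is one number in the SAP or a less favourable power statement, with no additional subjects and no change to conduct.
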